### 2.2 Study Description

#### 2.2.1 Study Design

The study is a phase IV, open-label, single-arm, multi-centre, prospective study to be conducted in India. The study will evaluate the safety and efficacy of Acalabrutinib in Indian adult Patients with CLL/SLL and Patients with MCL who have received at least one prior therapy. The Investigator will be trained on the locally approved Prescribing Information (PI) before the enrolment of the first Patient at their site to ensure compliance and proper dosing of the study drug. Patients will be monitored throughout the study period for AEs /SAEs/AESI of Acalabrutinib.

Patients with CLL/SLL and MCL who are eligible to receive Acalabrutinib treatment as per locally approved PI and ratified by an independent clinical judgment of treating physician will be evaluated for inclusion into the current phase IV trial. To enrol approximately 100 Patients (90 Patients of TN & R/R CLL and 10 R/R MCL Patients) into the study, it is expected that approximately 150 Patients will need to be screened.

The study will be initiated after approval by the Ethics Committee. Patients will undergo the following phases: Screening/Enrolment Phase, Treatment Phase, and Follow-up Phase.

Document Title:	Document ID:	BP04-01
Statistical Analysis Plan	Version Number:	3.1
	Effective Date:	25-Nov-2021

The decision of Patients to participate in this study must not, in any way, impact the standard of care they are receiving or any benefits to which they are otherwise entitled. Prior to data collection, all Patients must sign an Informed Consent Form (ICF), allowing for data collection and source data verification to be performed in accordance with local requirements and Sponsor policy.

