**b. MCL Patients:**

i. Confirmed MCL with translocation t(11;14) (q13;q32) and/or overexpressed cyclin D1

ii. Measurable nodal disease (one or more lesions measuring  $\geq 2$  cm in the longest diameter)

iii. Relapsed after, or were refractory to, 1-5 previous treatments.

[figure not shown]
Document Title:	Document ID:	BP04-01
Statistical Analysis Plan	Version Number:	3.1
	Effective Date:	25-Nov-2021

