- Treatment phase from Day 1 to Day 168. The treatment with Acalabrutinib will be continued until disease progression or unacceptable drug-related toxicity, whichever occurs earlier.
- The screening physical examination will include, at a minimum, the general appearance of the Patient, height (screening only) and weight, and examination of the skin, eyes, ears, nose, throat, lungs, heart, abdomen, extremities, musculoskeletal system, lymphatic system, and nervous system. Symptom-directed physical examination, including tumour assessments by palpation, are done thereafter.
- Vital signs (blood pressure, heart rate, and temperature) will be assessed after the Patient has rested in the sitting position.

Document Title:	Document ID:	BP04-01
Statistical Analysis Plan	Version Number:	3.1
	Effective Date:	25-Nov-2021

- d. Lymph node biopsy will be conducted in Patients with lymphadenopathy. However, a report of previous lymph node biopsy performed within 06 months before the study enrolment could be considered if the Patient did not receive any medication during that period

Study Phase	Screening Phase	Treatment Phase a		Follow-up Phase
Cycle		Cycles 1-6	EOT	EOS
Visit No.	1	2-7 (Day 1 of each cycle)	8	
Study Days	-6 to 0	1-168 (28 days per cycle)	170	28 days post-EOT

- e. Next-generation sequencing will be conducted to understand the genetic profile in Indian settings. Molecular cytogenetics (FISH) for del(13q), del(11q), del(17p), trisomy 12 in peripheral blood lymphocytes; TP53 mutation; immunoglobulin variable heavy chain (IGHV) mutational status will be assessed before the start of treatment in CLL/SLL-naïve Patients, or CLL/SLL Patients who did not have their report. However, MCL Patients are Relapsed/Refractory and their previous report data will be used. A six months old report can be considered for both the conditions.
- f. Haematology will include a complete blood cell count [white blood cell count, haemoglobin (Hb), haematocrit, reticulocyte, and platelet count] and differential leukocyte count, including both percent and an absolute number of lymphocytes. Haematology need not be repeated on Cycle 1 Day 1 if screening haematology was within 5 days.

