## 3. Population Analysis Set

### 3.1 Full Analysis Set

The Full Analysis Set (FAS) will consist of all enrolled Patients who received at least one dose of Acabrutinib.

Document Title:	Document ID:	BP04-01
Statistical Analysis Plan	Version Number:	3.1
	Effective Date:	25-Nov-2021

The FAS will be used for all analyses of safety and efficacy.

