**Table 14.1.5. Summary of Baseline Disease Characteristics**

	CLL/SLL (N=xx)	MCL (N=xx)	Total (N=xx)
	n (%)	n (%)	n (%)
Clinical Staging (Rai Staging) of Chronic Lymphocytic Leukaemia			
Stage 0	xx (xx.xx)	xx (xx.xx)	xx (xx.xx)
Stage I	xx (xx.xx)	xx (xx.xx)	xx (xx.xx)
Stage II	xx (xx.xx)	xx (xx.xx)	xx (xx.xx)
Stage III	xx (xx.xx)	xx (xx.xx)	xx (xx.xx)
Stage IV	xx (xx.xx)	xx (xx.xx)	xx (xx.xx)
Characteristics			
Only Blood abnormality	xx (xx.xx)	xx (xx.xx)	xx (xx.xx)
Blood abnormality with lymphadenopathy	xx (xx.xx)	xx (xx.xx)	xx (xx.xx)
Blood abnormality with organomegaly	xx (xx.xx)	xx (xx.xx)	xx (xx.xx)
CLL-IPi Score			
n	xx	xx	xx
Missing	xx	xx	xx
Mean (SD)	xx.x (xx.xx)	xx.x (xx.xx)	xx.x (xx.xx)
Median	xx.x	xx.x	xx.x
(min, max)	(xx.xx, xx.xx)	(xx.xx, xx.xx)	(xx.xx, xx.xx)
Mantle Cell Lymphoma			
Relapsed	xx (xx.xx)	xx (xx.xx)	xx (xx.xx)
Refractory	xx (xx.xx)	xx (xx.xx)	xx (xx.xx)
Clinical Staging (Ann Arber)			
Stage I	xx (xx.xx)	xx (xx.xx)	xx (xx.xx)
Stage II	xx (xx.xx)	xx (xx.xx)	xx (xx.xx)
Stage IE	xx (xx.xx)	xx (xx.xx)	xx (xx.xx)
Stage IIE	xx (xx.xx)	xx (xx.xx)	xx (xx.xx)
Stage III	xx (xx.xx)	xx (xx.xx)	xx (xx.xx)
Stage IIIS	xx (xx.xx)	xx (xx.xx)	xx (xx.xx)
Stage IIIE	xx (xx.xx)	xx (xx.xx)	xx (xx.xx)
Stage IV	xx (xx.xx)	xx (xx.xx)	xx (xx.xx)
Genomic alteration			
Translocation t(11;14) (q13;q32)	xx (xx.xx)	xx (xx.xx)	xx (xx.xx)
Overexpressed cyclin D1	xx (xx.xx)	xx (xx.xx)	xx (xx.xx)
MIPI Score			
n	xx	xx	xx
Missing	xx	xx	xx
Mean (SD)	xx.x (xx.xx)	xx.x (xx.xx)	xx.x (xx.xx)
Median	xx.x	xx.x	xx.x
(min, max)	(xx.xx, xx.xx)	(xx.xx, xx.xx)	(xx.xx, xx.xx)

- The Capital "N" in the column header represents the total number Full Analysis Set.
- The small "n" in summary statistics represents the total number of Patients.
- Percentages are based on number of patient in each group.
- SD = Standard Deviation, min=minimum, max=maximum
- Source :Listing 16.2.3.

Document Title:	Document ID:	BP04-01
Statistical Analysis Plan	Version Number:	3.1
	Effective Date:	25-Nov-2021

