**Table 14.1.6. Summary of Lymph Node Biopsy**

	CLL/SLL (N=xx)	MCL (N=xx)	Total (N=xx)
	n (%)	n (%)	n (%)
Lymph node enlarged			
Yes	xx (xx.xx)	xx (xx.xx)	xx (xx.xx)
No	xx (xx.xx)	xx (xx.xx)	xx (xx.xx)
Size of Lymph node (mm)			
n	xx	xx	xx
Missing	xx	xx	xx
Mean (SD)	xx.x (xx.xx)	xx.x (xx.xx)	xx.x (xx.xx)
Median (min, max)	xx.x (xx.xx, xx.xx)	xx.x (xx.xx, xx.xx)	xx.x (xx.xx, xx.xx)
Lymph node biopsy performed within 6 months before study enrolment			
Yes	xx (xx.xx)	xx (xx.xx)	xx (xx.xx)
No	xx (xx.xx)	xx (xx.xx)	xx (xx.xx)
Method of Biopsy			
Fine-needle aspiration biopsy	xx (xx.xx)	xx (xx.xx)	xx (xx.xx)
Core needle biopsy	xx (xx.xx)	xx (xx.xx)	xx (xx.xx)
Open (surgical) biopsy	xx (xx.xx)	xx (xx.xx)	xx (xx.xx)

- The Capital "N" in the column header represents the total number Full Analysis Set.
- The small "n" in summary statistics represents the total number of Patients.
- Percentages are based on number of patient in each group.
- SD = Standard Deviation, min=minimum, max=maximum
- Source :Listing 16.2.4.

Document Title:	Document ID:	BP04-01
Statistical Analysis Plan	Version Number:	3.1
	Effective Date:	25-Nov-2021

Table 14.1.7. Summary of Next Generation Sequencing\_CLL

	(N=xx)
	n (%)
Genomic sample collected for molecular cytogenetics (FISH)	
Yes	xx (xx.xx)
No	xx (xx.xx)
NA	xx (xx.xx)
Any genomic alteration observed	
Yes	xx (xx.xx)
No	xx (xx.xx)
If Yes	
11q deletion	xx (xx.xx)
13q deletion	xx (xx.xx)
17p deletion	xx (xx.xx)
12 addition	xx (xx.xx)
TP53 mutation	xx (xx.xx)
IGHV mutation	xx (xx.xx)
Other	xx (xx.xx)
Other 1	xx (xx.xx)
Other n	xx (xx.xx)

- The Capital "N" in the column header represents the total number Full Analysis Set.
- The small "n" in summary statistics represents the total number of Patients.
- Percentages in the "Genomic sample collected for molecular cytogenetics" and "Any Genomic alteration observed" rows are based on number of patient in each group.
- Percentages in the "If yes" rows are based on number of Patient Any genomic alteration observed.
- Source :Listing 16.2.5.

Document Title:	Document ID:	BP04-01
Statistical Analysis Plan	Version Number:	3.1
	Effective Date:	25-Nov-2021

Table 14.1.8. Summary of Chest X-Ray

	CLL/SLL (N=xx) n (%)	MCL (N=xx) n (%)	Total (N=xx) n (%)
Visit x			

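### SAP Table 14.1.7 (CLL genetic panel) divides the any-alteration rows by the Full Analysis Set instead of by CLL/SLL patients with a result, which, read literally, understates the share

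*SAP*

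**What the plan says.** Table 14.1.7 in SAP section 8 is titled for CLL and has a single, unsplit column. Three footnotes set its denominators:

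- Column N: "The Capital 'N' in the column header represents the total number Full Analysis Set".
- Sample and any-alteration rows: "Percentages in the 'Genomic sample collected for molecular cytogenetics' and 'Any Genomic alteration observed' rows are based on number of patient in each group".
- Individual lesions: "Percentages in the 'If yes' rows are based on number of Patient Any genomic alteration observed".

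SAP section 3.1 defines the set without regard to disease: "The Full Analysis Set (FAS) will consist of all enrolled Patients who received at least one dose of Acabrutinib". Section 2.2.1 gives the planned mix: "To enrol approximately 100 Patients (90 Patients of TN & R/R CLL and 10 R/R MCL Patients) into the study".

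Footnote e of SAP section 2.2.5 says who is tested on study. The cytogenetic and mutation markers "will be assessed before the start of treatment in CLL/SLL-naïve Patients, or CLL/SLL Patients who did not have their report". For MCL patients the same footnote relies on earlier reports, and it accepts six-month-old reports for both diseases. The sample item in Table 14.1.7 offers Yes, No and NA.

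Other SAP shells treat results differently. Table 14.1.9 bases pregnancy-test results on patients tested. Table 14.3.4.3 bases serology results on patients with a sample collected.

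**The concern.** A share with an alteration is meaningful only among patients in whom an alteration could have been found. The panel is a CLL/SLL panel, so MCL patients do not belong in its denominator, and neither do CLL/SLL patients with no result. Including either group treats the absence of a result as if it were the absence of an alteration.

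The protocol (Table 1 footnote e and section 4.1.1) says that the panel is run to describe the genetic profile of Indian patients. A reader who takes the any-alteration percentage as that description would take too low a figure. The size of the shortfall would depend on cohort mix and completeness of testing, not on biology. Since the SAP divides other test results by patients tested or sampled, the departure here looks like an oversight.

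**Working it through.** **Inputs from the documents.** Planned cohorts are 90 CLL/SLL and 10 MCL, so FAS = 90 + 10 = 100 if all are dosed. The denominators are those in the Table 14.1.7 footnotes.

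**Assumed inputs.** The documents give neither the true share p nor the number R of CLL/SLL patients with a result. I take p from 30% to 80% and R from 60 to 90. MCL patients, and CLL/SLL patients without a result, are taken as blank in the any-alteration item (neither Yes nor No).

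**Plan's own figure.** The documents state none for this share. As a check on the two denominators, Table 8 in protocol section 9.2 gives 30 events as 33.3% (23.74%, 44.05%) of 90 and 30.0% (21.24%, 39.98%) of 100. Both Clopper-Pearson intervals reproduce exactly.

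**Formula.** Printed share = p × R / N, with N = 100 (literal footnote) or N = 90 (if the column is read as CLL/SLL only). With R as denominator, the printed share is p.

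**Step 1: MCL patients alone (R = 90, N = 100).** The factor is 90/100 = 0.90.

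- p = 30%: 27/100 = 27%
- p = 60%: 54/100 = 54%
- p = 80%: 72/100 = 72%

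Yes and No together then add to 90%, not 100%. The printed share could not exceed 90% even if every CLL/SLL patient had an alteration.

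**Step 2: add CLL/SLL patients without a result (p = 50%).**

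| R | Patients with alteration | Over 100 | Over 90 | Over R |
|---|---|---|---|---|
| 90 | 45 | 45.0% | 50.0% | 50.0% |
| 80 | 40 | 40.0% | 44.4% | 50.0% |
| 70 | 35 | 35.0% | 38.9% | 50.0% |
| 60 | 30 | 30.0% | 33.3% | 50.0% |

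At R = 70, a true 30% prints as 21.0% over 100 or 23.3% over 90. A true 80% prints as 56.0% or 62.2%.

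**Step 3: rows not affected.** The individual lesion rows divide by patients with any alteration, so the FAS denominator does not enter them.

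**The case against.** The strongest reply is that N already means CLL/SLL patients. The N footnote is a stock line. It also stands under tables with separate CLL/SLL and MCL columns, where it can only mean the FAS patients of that cohort. The title of Table 14.1.7 names CLL, and its source, Listing 16.2.5, has no patient-group column, as one would expect of a CLL-only data set. This reading is plausible and would remove the MCL part of the dilution. It does not remove the second part: as the column over 90 shows, patients without a result still lower the share.

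It can also be said that few CLL/SLL patients should lack a result, because testing covers the treatment-naïve and those without a report, and earlier reports are accepted. A sample status of No or NA therefore does not by itself mean that there is no result. That is fair. The number is unknown and may be small; if it is zero and N is read as 90, there is no error.

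Finally, the counts are printed. With MCL patients and those without a result left blank, Yes/(Yes + No) recovers the share: 54/(54 + 36) = 60%. A reader might infer that the right figure is lost; in that case it is not.

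**Conclusion.** The point holds as a minor correction to a descriptive table. As written, the any-alteration rows are not restricted to patients with a result. Under the literal N, MCL patients alone lower the share by a tenth in relative terms (60% prints as 54%). Each CLL/SLL patient without a result lowers it further under either reading of N. These sizes rest on the planned 90 + 10, MCL entries left blank, and assumed values of p and R. Genetic profile is not a study objective or endpoint, and the planned safety and response analyses do not use this row.

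Two stronger readings are not supported:

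- **The share could be inflated.** A reader might infer that MCL reports would be counted as alterations, since eligibility requires "Confirmed MCL with translocation t(11;14) (q13;q32) and/or overexpressed cyclin D1". Nothing in the SAP sends those reports to Table 14.1.7. Table 14.1.5 has its own rows for both MCL markers, sourced from Listing 16.2.3.
- **Table 14.1.5 has the same fault.** Its footnote is similar ("Percentages are based on number of patient in each group"), but it has separate CLL/SLL and MCL columns that carry the right denominators. Whether to fill its Total column for disease-specific rows is a matter of layout.

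**What to change.** In Table 14.1.7:

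1. Head the column CLL/SLL and define N as CLL/SLL patients in the FAS.
2. Base the any-alteration rows on CLL/SLL patients with an available result, whether from a new sample or from an accepted earlier report. Patients sampled on study would be too narrow a base.
3. Add a row for CLL/SLL patients without a result, so that completeness is visible.
4. State that MCL reports are summarised in Table 14.1.5 and not here. Table 14.1.5 needs no change.

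The cost is a column header, footnote wording and one row in a single shell. No new data are needed. The any-alteration percentages will rest on a somewhat smaller denominator, which the new row will show.

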**Table 14.1.9. Summary of urine Pregnancy Test**

	CLL/SLL (N=xx)	MCL (N=xx)	Total (N=xx)
	n (%)	n (%)	n (%)
Visit x			
Urine Pregnancy Test Performed			
Yes	xx (xx.xx)	xx (xx.xx)	xx (xx.xx)
No	xx (xx.xx)	xx (xx.xx)	xx (xx.xx)
Result			
Positive	xx (xx.xx)	xx (xx.xx)	xx (xx.xx)
Negative	xx (xx.xx)	xx (xx.xx)	xx (xx.xx)

- The Capital "N" in the column header represents the total number Full Analysis Set.
- The small "n" in summary statistics represents the total number of Patients.
- Programmer Note Visit x: Visit 1 up to Visit 8.
- Percentage in the "Urine Pregnancy Test" row based on number of patient in each group.
- Percentages in the "Result" row are based on the number of Patient with urine Pregnancy Test performed in each group.
- Source :Listing 16.2.18.1

Document Title:	Document ID:	BP04-01
Statistical Analysis Plan	Version Number:	3.1
	Effective Date:	25-Nov-2021

**Table 14.2.1. Analysis of Objective Response**

	CLL/SLL (N=xx)	MCL (N=xx)	Total (N=xx)
	n (%)	n (%)	n (%)
Visit 5			
Response Assessment			
Complete Response (CR)	xx (xx.xx)	xx (xx.xx)	xx (xx.xx)
Partial Response (PR)	xx (xx.xx)	xx (xx.xx)	xx (xx.xx)
Partial Response with lymphocytosis (PR-L)	xx (xx.xx)	xx (xx.xx)	xx (xx.xx)
Objective response	xx (xx.xx)	xx (xx.xx)	xx (xx.xx)
95 % CI	(xx.x, xx.x)	(xx.x, xx.x)	(xx.x, xx.x)
Visit 8			
Response Assessment			
Complete Response (CR)	xx (xx.xx)	xx (xx.xx)	xx (xx.xx)
Partial Response (PR)	xx (xx.xx)	xx (xx.xx)	xx (xx.xx)
Partial Response with lymphocytosis (PR-L)	xx (xx.xx)	xx (xx.xx)	xx (xx.xx)
Objective response	xx (xx.xx)	xx (xx.xx)	xx (xx.xx)
95 % CI	(xx.x, xx.x)	(xx.x, xx.x)	(xx.x, xx.x)

- Objective response = Complete Response (CR) + Partial Response (PR) + Partial Response with lymphocytosis (PRL)
- Percentage in the "Reponse Assessment" are based on number of patient in each group.
- 95 % CI will be calculated based on clopper Pearson confidence interval method
- Source :Listing 16.2.9.2

Document Title:	Document ID:	BP04-01
Statistical Analysis Plan	Version Number:	3.1
	Effective Date:	25-Nov-2021

Table 14.2.2. Summary of QLQ-C30 Questionnaire

	CLL/SLL (N=xx) n (%)	MCL (N=xx) n (%)	MCL (N=xx) n (%)
Visit x			
Do you have any trouble doing strenuous activities, like carrying a heavy shopping bag or a suitcase			
1 (Not at all)	xx (xx.xx)	xx (xx.xx)	xx (xx.xx)
2 (A little)	xx (xx.xx)	xx (xx.xx)	xx (xx.xx)
3 (Quite a bit)	xx (xx.xx)	xx (xx.xx)	xx (xx.xx)
4 (Very much)	xx (xx.xx)	xx (xx.xx)	xx (xx.xx)
Do you have any trouble taking a long walk			
1 (Not at all)	xx (xx.xx)	xx (xx.xx)	xx (xx.xx)
2 (A little)	xx (xx.xx)	xx (xx.xx)	xx (xx.xx)
3 (Quite a bit)	xx (xx.xx)	xx (xx.xx)	xx (xx.xx)
4 (Very much)	xx (xx.xx)	xx (xx.xx)	xx (xx.xx)
Do you have any trouble taking a short walk outside of the house			
1 (Not at all)	xx (xx.xx)	xx (xx.xx)	xx (xx.xx)
2 (A little)	xx (xx.xx)	xx (xx.xx)	xx (xx.xx)
3 (Quite a bit)	xx (xx.xx)	xx (xx.xx)	xx (xx.xx)
4 (Very much)	xx (xx.xx)	xx (xx.xx)	xx (xx.xx)
Do you need to stay in bed or a chair during the day			
1 (Not at all)	xx (xx.xx)	xx (xx.xx)	xx (xx.xx)
2 (A little)	xx (xx.xx)	xx (xx.xx)	xx (xx.xx)
3 (Quite a bit)	xx (xx.xx)	xx (xx.xx)	xx (xx.xx)
4 (Very much)	xx (xx.xx)	xx (xx.xx)	xx (xx.xx)
Do you need help with eating, dressing, washing yourself or using the toilet			
1 (Not at all)	xx (xx.xx)	xx (xx.xx)	xx (xx.xx)
2 (A little)	xx (xx.xx)	xx (xx.xx)	xx (xx.xx)
3 (Quite a bit)	xx (xx.xx)	xx (xx.xx)	xx (xx.xx)
4 (Very much)	xx (xx.xx)	xx (xx.xx)	xx (xx.xx)
Were you limited in doing either your work or other daily activities			
1 (Not at all)	xx (xx.xx)	xx (xx.xx)	xx (xx.xx)
2 (A little)	xx (xx.xx)	xx (xx.xx)	xx (xx.xx)
3 (Quite a bit)	xx (xx.xx)	xx (xx.xx)	xx (xx.xx)
4 (Very much)	xx (xx.xx)	xx (xx.xx)	xx (xx.xx)
Were you limited in pursuing your hobbies or other leisure time activities			
1 (Not at all)	xx (xx.xx)	xx (xx.xx)	xx (xx.xx)
2 (A little)	xx (xx.xx)	xx (xx.xx)	xx (xx.xx)
3 (Quite a bit)	xx (xx.xx)	xx (xx.xx)	xx (xx.xx)
4 (Very much)	xx (xx.xx)	xx (xx.xx)	xx (xx.xx)
Were you short of breath			
1 (Not at all)	xx (xx.xx)	xx (xx.xx)	xx (xx.xx)
2 (A little)	xx (xx.xx)	xx (xx.xx)	xx (xx.xx)
3 (Quite a bit)	xx (xx.xx)	xx (xx.xx)	xx (xx.xx)
4 (Very much)	xx (xx.xx)	xx (xx.xx)	xx (xx.xx)
Have you had pain			

Document Title:	Document ID:	BP04-01
Statistical Analysis Plan	Version Number:	3.1
	Effective Date:	25-Nov-2021

3 (Quite a bit)	xx (xx.xx)	xx (xx.xx)	xx (xx.xx)
4 (Very much)	xx (xx.xx)	xx (xx.xx)	xx (xx.xx)
Did pain interfere with your daily activities			
1 (Not at all)	xx (xx.xx)	xx (xx.xx)	xx (xx.xx)
2 (A little)	xx (xx.xx)	xx (xx.xx)	xx (xx.xx)
3 (Quite a bit)	xx (xx.xx)	xx (xx.xx)	xx (xx.xx)
4 (Very much)	xx (xx.xx)	xx (xx.xx)	xx (xx.xx)
Have you had difficulty in concentrating on things, like reading a newspaper or watching television			
1 (Not at all)	xx (xx.xx)	xx (xx.xx)	xx (xx.xx)
2 (A little)	xx (xx.xx)	xx (xx.xx)	xx (xx.xx)
3 (Quite a bit)	xx (xx.xx)	xx (xx.xx)	xx (xx.xx)
4 (Very much)	xx (xx.xx)	xx (xx.xx)	xx (xx.xx)
Did you feel tense			
1 (Not at all)	xx (xx.xx)	xx (xx.xx)	xx (xx.xx)
2 (A little)	xx (xx.xx)	xx (xx.xx)	xx (xx.xx)
3 (Quite a bit)	xx (xx.xx)	xx (xx.xx)	xx (xx.xx)
4 (Very much)	xx (xx.xx)	xx (xx.xx)	xx (xx.xx)
Did you worry			
1 (Not at all)	xx (xx.xx)	xx (xx.xx)	xx (xx.xx)
2 (A little)	xx (xx.xx)	xx (xx.xx)	xx (xx.xx)
3 (Quite a bit)	xx (xx.xx)	xx (xx.xx)	xx (xx.xx)
4 (Very much)	xx (xx.xx)	xx (xx.xx)	xx (xx.xx)
Did you feel irritable			
1 (Not at all)	xx (xx.xx)	xx (xx.xx)	xx (xx.xx)
2 (A little)	xx (xx.xx)	xx (xx.xx)	xx (xx.xx)
3 (Quite a bit)	xx (xx.xx)	xx (xx.xx)	xx (xx.xx)
4 (Very much)	xx (xx.xx)	xx (xx.xx)	xx (xx.xx)
Did you feel depressed			
1 (Not at all)	xx (xx.xx)	xx (xx.xx)	xx (xx.xx)
2 (A little)	xx (xx.xx)	xx (xx.xx)	xx (xx.xx)
3 (Quite a bit)	xx (xx.xx)	xx (xx.xx)	xx (xx.xx)
4 (Very much)	xx (xx.xx)	xx (xx.xx)	xx (xx.xx)
Have you had difficulty remembering things			
1 (Not at all)	xx (xx.xx)	xx (xx.xx)	xx (xx.xx)
2 (A little)	xx (xx.xx)	xx (xx.xx)	xx (xx.xx)
3 (Quite a bit)	xx (xx.xx)	xx (xx.xx)	xx (xx.xx)
4 (Very much)	xx (xx.xx)	xx (xx.xx)	xx (xx.xx)
Has your physical condition or medical treatment interfered with your family life			
1 (Not at all)	xx (xx.xx)	xx (xx.xx)	xx (xx.xx)
2 (A little)	xx (xx.xx)	xx (xx.xx)	xx (xx.xx)
3 (Quite a bit)	xx (xx.xx)	xx (xx.xx)	xx (xx.xx)
4 (Very much)	xx (xx.xx)	xx (xx.xx)	xx (xx.xx)
Has your physical condition or medical treatment interfered with your social activities			
1 (Not at all)	xx (xx.xx)	xx (xx.xx)	xx (xx.xx)
2 (A little)	xx (xx.xx)	xx (xx.xx)	xx (xx.xx)

Document Title:	Document ID:	BP04-01
Statistical Analysis Plan	Version Number:	3.1
	Effective Date:	25-Nov-2021

**Table 14.3.1. Summary of Adverse Event**

	CLL/SLL (N=xx) n (%)	MCL (N=xx) n (%)	Total (N=xx) n (%)
Patient Experience Any Adverse Event			
Yes	xx (xx.xx)	xx (xx.xx)	xx (xx.xx)
No	xx (xx.xx)	xx (xx.xx)	xx (xx.xx)
CTCAE grade			
Mild	xx (xx.xx)	xx (xx.xx)	xx (xx.xx)
Moderate	xx (xx.xx)	xx (xx.xx)	xx (xx.xx)
Severe	xx (xx.xx)	xx (xx.xx)	xx (xx.xx)
Life – Threatening or disabling	xx (xx.xx)	xx (xx.xx)	xx (xx.xx)
Death	xx (xx.xx)	xx (xx.xx)	xx (xx.xx)
Investigator’s causality rating against the Investigational Product			
Yes	xx (xx.xx)	xx (xx.xx)	xx (xx.xx)
No	xx (xx.xx)	xx (xx.xx)	xx (xx.xx)
Action Taken			
None	xx (xx.xx)	xx (xx.xx)	xx (xx.xx)
Non-drug treatment required	xx (xx.xx)	xx (xx.xx)	xx (xx.xx)
Hospitalization/ prolonged hospitalization	xx (xx.xx)	xx (xx.xx)	xx (xx.xx)
Diagnostic or clinical test(s) conducted	xx (xx.xx)	xx (xx.xx)	xx (xx.xx)
Drug Withdrawn	xx (xx.xx)	xx (xx.xx)	xx (xx.xx)
Patient Withdrawn			
Yes	xx (xx.xx)	xx (xx.xx)	xx (xx.xx)
No	xx (xx.xx)	xx (xx.xx)	xx (xx.xx)
Treatment taken			
Yes	xx (xx.xx)	xx (xx.xx)	xx (xx.xx)
No	xx (xx.xx)	xx (xx.xx)	xx (xx.xx)
Outcome			
Recovered without sequelae	xx (xx.xx)	xx (xx.xx)	xx (xx.xx)
Recovered with sequelae	xx (xx.xx)	xx (xx.xx)	xx (xx.xx)
Not recovered/ Not resolved	xx (xx.xx)	xx (xx.xx)	xx (xx.xx)
Recovering/ resolving	xx (xx.xx)	xx (xx.xx)	xx (xx.xx)
Unknown	xx (xx.xx)	xx (xx.xx)	xx (xx.xx)
Fatal	xx (xx.xx)	xx (xx.xx)	xx (xx.xx)

- The Capital "N" in the column header represents the total number Full Analysis Set.
- The small "n" in summary statistics represents the total number of Patients.
- Percentages in the "Patient Experience Any Adverse Event" rows are based on number of patient in each group.
- Percentages in the "CTCAE grade, Investigator’s causality rating against the Investigational Product, Action Taken, Patient Withdrawn, Treatment taken and Outcome" rows are based on number of Patient Experience Any Adverse Event in each group.
- Source :Listing 16.2.11.1, Listing 16.2.11.2

Document Title:	Document ID:	BP04-01
Statistical Analysis Plan	Version Number:	3.1
	Effective Date:	25-Nov-2021

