6.4 Treatment compliance

Any change from the dosing schedule: dose interruptions, dose reductions, dose discontinuations should be recorded in the eCRF. There should be 100% compliance with the study medication. No drug interruptions and missed doses will be permitted in the study.

The Investigational Product Storage Manager(Investigator/delegate) is responsible for managing the IMP from receipt by the study site until the destruction or return of all unused IMP. The Investigator(s) is responsible for ensuring that the patient has returned all unused IMP.

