8.2.4 Adverse event data collection

The following variables will be collected for each AE;

- AE (verbatim).
- The date and time when the AE started and stopped.
- CTCAE grade 3 or more: whether the AE is serious or not
- Investigator's causality rating against the Investigational Product (yes or no).
- Action taken with regards to Investigational Product(s).
- Select the appropriate as required: AE caused patient's withdrawal from study (yes or no).
- Outcome.

In addition, the following variables will be collected for SAEs:

- Date AE met criteria for serious AE
- Date Investigator became aware of serious AE
- Reason for AE becoming serious
- Date of hospitalisation
- Date of discharge
- Probable cause of death
- Date of death

- Autopsy performed
- Causality assessment in relation to study procedure(s)
- Causality assessment to other medication/s

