Appendix C Recommended Treatment Modifications for Acalabrutinib and Management Recommendations

Recommended dose modifications of Acalabrutinib for Grade ≥ 3 adverse reactions are provided in Table 9.

The administration of Acalabrutinib must be temporarily interrupted to manage a Grade ≥ 3 non-haematological treatment-related adverse reaction, Grade 3 thrombocytopenia with significant bleeding, Grade 4 thrombocytopenia, or Grade 4 neutropenia lasting longer than 07 days. Upon resolution of the adverse reaction to Grade 1 or baseline (recovery), administration of Acalabrutinib must be restarted as recommended in Table 9.

Table 9: Recommended Dose Adjustments for Adverse Reactions*

Adverse Reaction Occurrence	Dose Modification (Starting dose = 100 mg twice daily)
1 st and 2 nd	Restart at 100 mg twice daily
3 rd	Restart at 100 mg daily
4 th	Discontinue Acalabrutinib

*Adverse reactions graded by the National Cancer Institute Common Terminology Criteria for Adverse Events (NCI CTCAE) version 4.03.

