**Listing 16.2.7.3. Listing of Patient Treatment Compliance**

Patient Number	Visit	Patient Group	Any change from the dosing schedule	If Yes, comment	Patient 100% compliant with the treatment medication in last treatment cycle
xx-xxxx	xxxx	(CLL/SLL)/(MCL)	Yes/No	Xxxx	Yes/No
xx-xxxx	xxxx	(CLL/SLL)/(MCL)	Yes/No	Xxxx	Yes/No
xx-xxxx	xxxx	(CLL/SLL)/(MCL)	Yes/No	xxxx	Yes/No
xx-xxxx	xxxx	(CLL/SLL)/(MCL)	Yes/No	Xxxx	Yes/No
xx-xxxx	xxxx	(CLL/SLL)/(MCL)	Yes/No	xxxx	Yes/No

Document Title:	Document ID:	BP04-01
Statistical Analysis Plan	Version Number:	3.1
	Effective Date:	25-Nov-2021

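### The SAP's adverse event table has no row for study drug interrupted or dose reduced, so no planned table can count AEs that lead to either

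*SAP*

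**What the plan says.** Protocol 8.2.4 lists the variables collected for every AE. One is "Action taken with regards to Investigational Product(s", that is, what was done with the study drug. Protocol 6.4 adds a recording duty: "Any change from the dosing schedule: dose interruptions, dose reductions, dose discontinuations should be recorded in the eCRF". Appendix C says of specified severe reactions that "The administration of Acalabrutinib must be temporarily interrupted to manage" them. Its Table 9 then gives a restart at the starting dose after the first and second occurrence, a restart at a lower daily dose after the third, and discontinuation at the fourth.

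SAP Table 14.3.1 shortens the variable to Action Taken and fixes its rows: None, "Non-drug treatment required", "Hospitalization/ prolonged hospitalization", "Diagnostic or clinical test(s) conducted" and "Drug Withdrawn". There is no row for interrupted, reduced or other. A footnote bases the percentages in this block on patients with any AE, not on the Full Analysis Set (FAS).

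SAP section 1 states that where the SAP differs from the protocol's analysis, the SAP prevails. SAP 6.3.1 says only that AEs are summarised by frequencies and percentages, so the table shell is the working specification.

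**The concern.** Safety is the primary objective, and Table 14.3.1 is the only AE summary table. AEs that stop or lower dosing without ending treatment lie between AEs with no effect on dosing and AEs that lead to withdrawal. How often they occur is a core tolerability result. It also bears on causality: the guide in Appendix B 7 asks whether the event improved when the drug was stopped or its dose lowered.

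The SAP's rows mix two questions: what was done with the drug, and how the event was managed. Only permanent withdrawal answers the first. If the shell is programmed as written, AEs leading to interruption or reduction cannot be classified correctly. SAP 2.5 plans all the primary safety analysis for an interim report on the first 50 completers as well, so the gap would affect two reports.

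**Working it through.** No sample size, rate or interval is involved. The check sets the drug actions in the protocol against the rows in the SAP.

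| Drug action | Where the protocol has it | Matching Action Taken row |
|---|---|---|
| Interruption | 6.4; Appendix C text | no row |
| Reduction, or restart at a lower daily dose | 6.4; Appendix C Table 9, third occurrence | no row |
| Discontinuation | 6.4; Appendix C Table 9, fourth occurrence | "Drug Withdrawn" |

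**Count.** There are five rows: one about the study drug, three about other management, and None (1 + 3 + 1 = 5). No row is for interruption, reduction or other. One of the three drug actions can be tabulated.

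**Where such an AE could go.** With no correct row there are four possibilities:
- None;
- one of the three non-drug rows;
- "Drug Withdrawn", if a temporary stop is read as a withdrawal;
- no row, so that it drops out of the block.

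The documents do not show which would happen. The eCRF code list is not among them, and the Action Taken column in Listing 16.2.11.2, a source for the table, is an undefined field.

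**Whether another output fills the gap.**
- The SAP's list of tables has no exposure or dose-modification table.
- Listings 16.2.7.1 and 16.2.7.2 show capsules dispensed and whether drug was given at the visit. They have no dose-change dates.
- Listing 16.2.7.3 has a Yes/No for any dosing change, a free-text comment, and a second Yes/No headed "Patient 100% compliant with the treatment medication in last treatment cycle". It is by patient and visit and has no AE identifier.
- Listings 16.2.11.1 and 16.2.11.2 give each AE's preferred term, start and end, grade, causality and action, also by patient and visit.

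A reader could match the comment in Listing 16.2.7.3 to an AE by patient, visit and date. Whether that works depends on what the site wrote. This is partial tracing, and it yields no incidence.

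**Denominator.** If k patients have an AE leading to interruption, A patients have any AE and N are in the FAS, this block would show k/A. The incidence among treated patients is k/N. Because A cannot exceed N, k/A is at least as large as k/N. Adding rows alone would therefore not give the incidence among treated patients; an FAS percentage is also needed.

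**The case against.** The strongest reply is that the protocol itself can be read as excluding these actions. Section 6.4 goes on to say that interruptions and missed doses are not permitted, and 6.1 advises against dose reduction. On that text the missing rows look deliberate. But the synopsis and 6.6 recommend escalation or reduction, 6.1 allows for withholding doses, and Appendix C contains interruption and a lower-dose restart. These passages conflict and must be reconciled; no view is taken here on which is right. The reporting gap does not depend on the answer, because 6.4 requires such changes to be recorded when they happen.

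A second reply is that no section promises the incidence of AE-led interruption or reduction. The primary outcome names reasons for discontinuation, and discontinuation is tabulated in Tables 14.1.1 and 14.3.1. That is true, so this is not a missing named endpoint. It is a collected AE variable whose summary cannot hold its own values.

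Three stronger readings are tempting, and the documents do not support them:
- **That tolerability will look better than it was.** This follows if the events go to None or a non-drug row. If they go to "Drug Withdrawn", tolerability looks worse. The direction is unknown.
- **That the information is lost or the events are hidden.** The listings allow partial tracing, and the triggering severe events still appear in the CTCAE grade rows of the same table.
- **That a given number of patients will be misclassified.** The documents give no interruption or reduction rate, so any count would be invented.

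**Conclusion.** The point holds as a reporting gap. Followed as written, the only planned AE summary table has no correct place for an AE that leads to interruption or reduction, and no planned table gives the incidence of either. Its size can be stated only structurally: one of three kinds of drug action is tabulated.

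The finding rests on the Table 14.3.1 shell being programmed as shown. An eCRF code list that already has the missing categories would make the repair easier, but would not by itself put them in the table. The change should be made before the safety tables are produced, because it concerns the primary objective and is inexpensive.

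**What to change.** In Table 14.3.1 and Listing 16.2.11.2, replace the single Action Taken item with two:
- action taken with acalabrutinib: dose not changed, interrupted, reduced, permanently withdrawn, not applicable;
- other management: none, non-drug treatment, hospitalisation, tests.

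Align the eCRF code list with the first item. Report the number and percentage of FAS patients with at least one AE leading to interruption, to reduction and to withdrawal. These are reporting categories and imply nothing about which dose changes should be allowed.

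The cost is a shell edit, possibly a code-list update, and recoding of AEs already entered. Recoding may need retrospective site queries: the protocol estimates the last patient's last visit in Q4 2021, and the SAP header carries an effective date of 25-Nov-2021, which may be a template date. Sections 6.4 and 8.2.4 already require the underlying facts to be collected.

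A redesigned dosing listing or an exposure table would be a useful addition, but is not needed to close this gap.

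Separately, the sponsor should reconcile the protocol passages on interruption and reduction: the dosage paragraph of the synopsis, 6.1, 6.4, 6.6 and Appendix C.
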